Effect modifiers

We will examine potential effect modification by reporting stratified results by age (as a categorical variable), sex and educational level.

Data sources and measurement

[figure not shown]
Data sources and measurements for all variables were described above. More details on the exact variables can be found in the Supplementary Appendix.

Bias

Confounding bias

We will reduce the risk of confounding by adjusting for potential confounders that causally precede the exposure and are associated with the outcome. We built a directed acyclic graph to guide the identification of potential confounders and mediators (Figure 1). Adjusting for mediators can result in an underestimation of the association and potentially introduce M-bias (a type of collider bias).^{31,32}

Figure 1. Directed acyclic graph of the causal association between tobacco use and COVID-19 vaccinations uptake

A special concern were participants who had a COVID-19 infection. Tobacco use is associated with COVID-19 infection and, in turn, having a COVID-19 infection can influence the willingness to vaccinate or delay COVID-19 vaccination. Current Finnish guidelines recommend to the general adult population, after having a COVID-19 infection, to: (i) wait at least two months before getting the first COVID-19 dose, (ii) wait at least four to six months after the COVID-19 infection or the first dose, whichever happens first. People with two doses will not be given a third dose if they have had COVID-19. Having a COVID-19 infection, according to our DAG, would act as a mediator. Excluding individuals who have had the infection (or adjusting for it) would result in estimating the direct effect between tobacco use and COVID-19 vaccination uptake and not the total effect. For this reason, our main analyses will report the outcomes without adjusting for having a COVID-19 infection. In sensitivity analyses, we will report estimates stratified by COVID-19 infection status and also we will use causal inference methods (e.g. marginal structural methods and G-formula) to account for this time-varying estimate. We expect, however, that this will not make a large difference, as the COVID-19 incidence prior to the start of the COVID-19 vaccinations was very low and continued to be low until the rise of the Omicron variant in mid-December 2021.³³ In practice, this means that a very small proportion of our sample will experience a COVID-19 infection during the study period.

Selection bias

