We described the categorisation of exposures and confounders above. We will model age as a continuous variable and tested non-linearity by comparing the linear model with penalised smoothing splines using a likelihood ratio test.³⁵ The variable years of education will be modelled as categorical to be able to account for secular changes in years of education during the study years. In other words, educational attainment increases over time and it is therefore more appropriate to calculate the educational attainment within each survey wave.

Statistical methods

We will use Poisson regression with robust standard errors to estimate the relative risk of confirmed COVID-19 cases. We will fit the following Poisson model:

$$(1) \quad \log \mu_i = \beta_0 + \beta_1 S_i + \beta_x X_i^* + \rho_1 R_a$$

where i denotes the individual, β_0 is the intercept; β_1 is the coefficient of interest for exposure to tobacco S ; a vector of covariates X^* (i.e., sex, age, marital status, years of education, mother tongue and participation in social activities); and fixed effects $\rho_1 R_a$ for wellbeing area a . We will report the exponentiated coefficient as the relative risk estimate for unadjusted and adjusted models with their corresponding 95% confidence intervals.

We will examine non-linearity between age and the outcome by comparing the linear model with penalised smoothing splines³⁵ using a likelihood ratio test with the Wald method.³⁶ We will use the model with splines if it performs better than the linear model, using a p-value of 0.05 as the threshold for this decision.

We will examine potential effect modification by reporting stratified analyses by age, sex and educational level. If there are noticeable differences, we will test for multiplicative interactions between tobacco use and sex, age and educational level by including an interaction term in equation 1. We will introduce the interaction terms one by one for each of the examined interactions. We will use a likelihood ratio test to compare the model with and without the interaction. A p-value lower than 0.05 in the likelihood ratio test will be used as an indication of the presence of an interaction. If there is evidence of an statistically significant interaction, we will include the interaction term in the final model.

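### A significant interaction goes into the final model, but the plan does not say how the overall tobacco RR is then obtained, so its target can depend on a test and on coding

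*Combined protocol and SAP*

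**What the plan says.** In the combined protocol and SAP, Statistical methods gives a log-linear model with main effects only (equation 1). Its tobacco coefficient "is the coefficient of interest for exposure to tobacco S". On reporting it says: "We will report the exponentiated coefficient as the relative risk estimate for unadjusted and adjusted models with their corresponding 95% confidence intervals".

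Two paragraphs later the same section sets out a chain for effect modification:

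- Stratified analyses come first. "If there are noticeable differences, we will test for multiplicative interactions between tobacco use and sex, age and educational level". The plan gives no criterion for what counts as noticeable.
- On order of entry: "We will introduce the interaction terms one by one for each of the examined interactions".
- On the threshold: "A p-value lower than 0.05 in the likelihood ratio test will be used as an indication of the presence of an interaction".
- On the consequence: "If there is evidence of an statistically significant interaction, we will include the interaction term in the final model".

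The scale of age differs between sections. Quantitative variables says "We will model age as a continuous variable", with splines if they fit better. Effect modifiers plans "reporting stratified results by age (as a categorical variable), sex and educational level". The plan does not state the scale on which age enters its interaction term, and it mentions no centring, reference level or marginal standardisation.

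**The concern.** The study asks whether tobacco use is associated with vaccine uptake in a nationally representative sample. That calls for one RR per tobacco category and outcome, with the same meaning throughout. The plan names a coefficient as that RR and then allows a test result to change the model in which the coefficient sits. With a product term in the model, the same symbol answers a different question.

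Two exposures, three modifiers and five outcomes (one primary, four secondary) give 2 × 3 × 5 = 30 places where the rule could act. It could act for smoking but not snus, or for one dose but not the next. RRs in the same table would then refer to different groups without being labelled so. The plan also does not say what happens if two modifiers, each entered alone, both pass the test. If both terms went in, the coefficient would refer to a cell defined by two reference levels.

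**Working it through.** The plan gives no effect size, power or sample-size figure on this point, so there is nothing of its own to reproduce. The check is algebra plus illustrations. **All effect sizes, exposure prevalences and age distributions below are assumptions.** From the documents come the age range (20 and over), the two analytical samples (14,736 + 28,199 = 42,935) and second-dose coverage of 87.6%. The simulations use no weights or imputation.

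**1. Algebra.** With log μ = b0 + b1·S + b2·M + b3·S·M, the tobacco RR at M = m is exp(b1 + b3·m). So exp(b1) is the RR at m = 0. For sex or education that is the reference level. For continuous, uncentred age it is age 0, outside a sample that starts at 20. With age bands it is the reference band. With a spline it depends on the basis.

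**2. Sex.** Assume RR 0.96 in women and 0.90 in men, 14% exposed, n = 42,935, Poisson model with robust standard errors.

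| Model | exp(b1) | 95% CI |
|---|---|---|
| No product term | 0.929 | 0.918 to 0.941 |
| Product term, women as reference | 0.961 | 0.946 to 0.977 |
| Product term, men as reference | 0.898 | 0.881 to 0.916 |

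The last two rows are the same fit to the same data. Only the coding differs.

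**3. Age, modest interaction.** Assume RR 0.93 at age 55, rising by a factor 1.01 per 10 years. The RR at age 0 is 0.93 × 1.01^(−5.5) = 0.880. In one simulated data set:

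- no product term: 0.933 (0.923 to 0.944);
- product term, uncentred age: 0.889 (0.857 to 0.921);
- product term, age centred at its mean: 0.933 (0.922 to 0.944);
- marginally standardised RR from the interaction model: 0.933.

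**4. Why an RR interaction is plausible here.** Uptake is high, so even a constant odds ratio (OR) forces the RR to change as baseline uptake changes. Take OR 0.6 with uptake in the unexposed of 80% at age 30 and 96% at age 80:

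- age 30: odds 4 × 0.6 = 2.4, uptake 2.4/3.4 = 0.706, RR 0.706/0.80 = 0.88;
- age 80: odds 24 × 0.6 = 14.4, uptake 14.4/15.4 = 0.935, RR 0.935/0.96 = 0.97.

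In simulations of this setting (13% exposed, ages uniform 20 to 90), exp(b1) is 0.936 without the product term and 0.842 with it if age is uncentred, with a standard error 3.7 times larger. Centred, it is 0.932, with a standard error ratio of 1.06.

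**5. How often the rule would fire.** This depends on the test, and the plan does not say whether its likelihood ratio test is adjusted for the survey design. In 40-replicate runs of the setting in step 4, a robust test gave p < 0.05 in 100% of replicates at OR 0.6 and 95% at OR 0.75. An ordinary Poisson likelihood ratio test did so in about 83% and 8%, and in as few as 55% and 0% in further runs that also varied the assumed age distribution.

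**The case against.** The strongest reply is that the reporting sentence directly follows equation 1, which has no product terms, and that nothing expressly carries it over to an interaction model. That is fair. A reader might infer that the plan commits to publishing a bare reference-group coefficient as its headline, but the documents do not say so. They leave open how the RR is obtained after the rule fires. The rule itself is nevertheless stated, and no sentence keeps a main-effects or standardised RR as the headline, so the gap remains.

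Second, stratified results by age, sex and education are promised whatever the tests show, and the code will be published. Readers would therefore see subgroup RRs and could trace the coding. This softens the harm, but it does not define the overall RR in advance.

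Third, a reader might infer that the headline will be an RR at age 0. That needs continuous age, no centring and a bare coefficient. The scale of the age interaction is not stated, and Effect modifiers treats age as categorical, so this is only one possible reading.

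Fourth, a reader might compute the chance of at least one false trigger as 1 − 0.95^6 = 26.5% for the primary outcome or 1 − 0.95^30 = 78.5% over all five. Those figures require every test to be run, independent and of true 5% size. The plan tests only where strata look different. For a common binary outcome the ordinary Poisson likelihood ratio test is also far below 5%: at 87.6% uptake its statistic is about 0.124 times a chi-square, so its true size is P(χ² > 3.84/0.124 = 31.0), about 3 × 10⁻⁸. The figures should not be quoted without those conditions.

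Finally, including a supported interaction and reporting level-specific RRs is accepted practice. The objection here is only to leaving the overall RR undefined when that is done.

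**Conclusion.** The concern holds as a gap in how the reported RR is defined. A data-driven rule can alter the final model, and the plan does not say which RR is then the main result. The algebra holds for every tobacco coefficient (three for smoking, two for snus) and for any test.

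The size rests on assumptions. An assumed sex interaction moves the figure by about 0.03 either way from 0.929, purely through the choice of reference. The larger age shift, from about 0.94 to 0.84, arises only with uncentred continuous age and almost disappears on centring. No firm trigger rate can be given, because the version of the test and the threshold for noticeable differences are not specified. The illustrations use the full combined sample and ages up to 90. They do not carry over numerically to snus, which was recorded only at ages 20 to 74. Priority: should fix.

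**What to change.** Replace the last sentence of the interaction paragraph in Statistical methods with wording such as:

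> The reported RR for every primary and secondary outcome comes from equation 1 without product terms, whatever the interaction tests show. Each interaction is fitted in a separate model and presented as RRs with 95% confidence intervals at every level of the modifier, using the same age bands as the stratified results.

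If the authors prefer to keep supported interactions in the final model, a marginally standardised RR from that model, named in advance as the headline, does the same job.

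Running and reporting all six interaction tests on the primary outcome (two exposures × three modifiers), instead of only those that look different, would remove the undefined screen. It is optional and not needed to settle the meaning of the RR.

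The cost is a change of wording and a few extra table rows. No new data are needed.

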Smokers are at higher risk of COVID-19 hospitalizations and deaths⁸ and might thus benefit greatly from high vaccination coverage. However, evidence suggests that they may be less likely to be vaccinated, as smokers are less likely to adhere to preventive measures in general and have lower adherence to other vaccines.^{9,10} Reports of a protective role of smoking on the risk of COVID-19 infection might have also reduced the perceived risks from being infected¹¹. Evidence regarding tobacco use and COVID-19 vaccine hesitancy is mixed. Some studies have shown greater mistrust in COVID-19 vaccine benefits¹¹⁻¹⁴ and greater vaccine hesitancy and lower vaccine acceptance compared to non-smokers,^{11,15,16} while other studies have reported no differences by smoking status or lower levels of vaccine hesitancy in smokers compared to non-smokers.¹⁷⁻²⁰

Vaccine uptake, however, is a dynamic process not only influenced by trust and risk perception, but by convenience factors related to physical and geographical availability, affordability, ability to understand and appeal of immunisation services.²¹ To our knowledge, two studies from convenience samples in Singapore and Palestine have examined vaccination uptake by smoking status.^{22,23} Both studies showed that smokers had higher odds of being vaccinated.^{22,23} However, these studies are not representative of the general population and relied on self-reported vaccination status, resulting in a higher risk of selection and information bias. Spacing between vaccine doses is also relevant, as a growing body of literature suggests that smokers develop a weaker immune response to COVID-19 vaccines.²⁴

Finland developed a national COVID-19 vaccination strategy and the vaccine rollout started on December 27, 2020. Vaccinations started with priority groups (health and social care personnel and people at high risk of severe COVID-19) but eventually were expanded to the whole population aged 5 and over.²⁵ COVID-19 vaccines are provided free of charge and delivered nationwide by each municipality. Finland has administered primarily mRNA vaccines (Cominarty and Spikevax).²⁵ Vaccination coverage in the Finnish population aged 18 and older has reached 89.7% for the first dose, 87.6% for the second dose and 65.1% for the booster dose by June 14, 2022.²⁶

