Participants in the FinSote 2020 Survey were adults aged 20 and over derived from the Digital and Population Data Services Registry, created in Jan 2020 after the merge between the Population Register of Statistics Finland and local register offices.²⁹ This sampling frame includes all residents in Finland. The survey was based on a stratified random sample of 22 regions (2000 adults aged 20-74, 800 adults aged 75+, total sample size 61600). Data collection started on September 14, 2020, and finished on February 8, 2021. Participants received a self-administered questionnaire in Finnish, Swedish, English or Russian, which could be returned on paper or filled in electronically. The analytical sample is 28199 participants, with a participation rate of 46%. In 2020, consent to linkage was included in the overall consent, and as a result, we were able to link all participants in the analytical sample.

We will link data from FinSote 2018 and 2020 surveys to the Finnish National Vaccination Register maintained by the Finnish Institute for Health and Welfare using a unique identifier assigned to all residents in Finland. The follow-up will be between December 27, 2020 (date of the first COVID-19 vaccination in the country) until May 31, 2022 or the latest available date.

Outcomes

Our primary outcome will be the vaccination uptake of at least two doses of a COVID-19 vaccine. We will examine four secondary outcomes:

- (i) vaccination uptake of at least one dose of a COVID-19 vaccine,
- (ii) vaccination uptake of the complete COVID-19 vaccination scheme (two doses and a booster dose),
- (iii) proportion of participants with more than 7 months between the first and second COVID-19 dose, and
- (iv) proportion of participants with more than 7 months between second dose and booster dose.

We will include any approved COVID-19 vaccination in Finland by the latest available date (i.e. April 29, 2022):³⁰ COVID-19 mRNA vaccines (Comirnaty and Spikevax), recombinant vaccines (Vaxzevria, COVID-19 vaccine Janssen, COVISHIELD, Nuvaxovid, COVOVAX), and inactivated vaccines (BIBP/Sinopharm, COVAXIN, Coronavac). Participants who have received the COVID-19 vaccine Janssen would be excluded from analyses on the second dose, as the vaccine only requires a single dose.

Exposures

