Our primary method to handle missing data will be multiple imputation, given that a missing at random assumption is the most likely in our data. We will examine patterns of missing data and use multiple imputation using chained equations (MICE). This procedure will be combined with the survey design tools to take the complex sampling design into account.

In sensitivity analyses, we will report estimates using complete case analyses (i.e. taking only the complex sampling design into account). We will also report the same estimates as the main analyses, but restricting the follow-up time to when vaccination coverage reached 60% and 80%. This will allow us to understand whether these associations changed over time and also provide estimates that might be comparable to countries with lower vaccination coverage, thus increasing the external validity of our estimates.

We will analyse the data using R version 4.1.1 and include the statistical code as a Supplementary Appendix.

References

- 2 Davies, N. G. *et al.* Estimated transmissibility and impact of SARS-CoV-2 lineage B.1.1.7 in England. *Science* **372**, eabg3055, doi:doi:10.1126/science.abg3055 (2021).
- 3 Campbell, F. *et al.* Increased transmissibility and global spread of SARS-CoV-2 variants of concern as at June 2021. *Euro Surveill* **26**, doi:10.2807/1560-7917.Es.2021.26.24.2100509 (2021).
- 4 Suthar, A. B. *et al.* Public health impact of covid-19 vaccines in the US: observational study. *BMJ* **377**, e069317, doi:10.1136/bmj-2021-069317 (2022).
- 5 Krause, P. R. *et al.* SARS-CoV-2 Variants and Vaccines. *New England Journal of Medicine* **385**, 179-186, doi:10.1056/NEJMsr2105280 (2021).
- 7 Kuodi, P. *et al.* Association between vaccination status and reported incidence of post-acute COVID-19 symptoms in Israel: a cross-sectional study of patients tested between March 2020 and November 2021. *medRxiv*, 2022.2001.2005.22268800, doi:10.1101/2022.01.05.22268800 (2022).

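### The 60% and 80% coverage analyses do not exempt the between-dose spacing outcomes, whose estimates at those cut-offs would be empty or would partly reflect the shortened window

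*Combined protocol and SAP*

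**What the plan says.** The Setting and participants section fixes the observation window: "The follow-up will be between December 27, 2020 (date of the first COVID-19 vaccination in the country) until May 31, 2022". It allows a different end if the data run to another date.

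The Outcomes section names uptake of at least two doses as primary and adds: "We will examine four secondary outcomes". Two of these concern uptake. The other two concern spacing. Outcome (iii) is the "proportion of participants with more than 7 months between the first and second COVID-19 dose". Outcome (iv) applies the same threshold one dose later: "proportion of participants with more than 7 months between second dose and booster dose".

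Under Confounding bias, the plan says that "our main analyses will report the outcomes without adjusting for having a COVID-19 infection".

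The last part of Statistical methods ends follow-up at two levels of coverage: "We will also report the same estimates as the main analyses, but restricting the follow-up time to when vaccination coverage reached 60% and 80" per cent. It gives two reasons. The first is "This will allow us to understand whether these associations changed over time"; the second is comparability with countries where coverage is lower. It does not say which dose or population defines coverage, gives no calendar dates for the two levels, and sets no eligibility window for the spacing outcomes.

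**The concern.** A spacing outcome can be seen only if both doses, and the 7 months between them, lie inside follow-up. Ending follow-up early is harmless to the definition of an uptake outcome, which simply asks who had been vaccinated by that date. It is not harmless to an outcome that takes more than 7 months to occur.

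If the cut-off is early enough, the Poisson model for (iii) and (iv) has no events in any tobacco group. If it is later, the model runs and returns a relative risk, but only people vaccinated early can contribute events. The introduction says the rollout began with priority groups, and the Information bias section says that supply was limited in the first months, so these people are not a random part of the sample. The plan intends to compare the cut-off results with the full-period result to judge change over time. For spacing, that comparison mixes any real change with a change in who can be positive.

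**Working it through.** **Inputs from the documents.** Start of follow-up S = 27 December 2020; planned end 31 May 2022, which is 520 days; gap required, more than 7 months. The documents state no figure of their own to reproduce on this point.

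**Earliest observable event.** S + 7 months = 27 July 2021 (day 212), so a dose 1 to dose 2 gap of more than 7 months first becomes observable on 28 July 2021. For dose 2 to booster, a second dose must come first. The documents give no minimum interval between doses 1 and 2. Assuming 3 weeks gives 18 August 2021; assuming 12 weeks gives 22 October 2021.

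**Window at cut-off C.** Let L = C minus 7 calendar months. Only an earlier dose given before L can show the gap. For (iii), eligible days = max(0, L − S) and share = (L − S)/(C − S). For (iv), the assumed minimum interval (21 or 84 days) is also subtracted.

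| Cut-off C | (iii): eligible days / window | Share | (iv): eligible days, 3-week / 12-week assumption |
|---|---|---|---|
| 27 July 2021 | 0 / 212 | 0% | 0 / 0 |
| 31 August 2021 | 35 / 247 | 14% | 14 / 0 |
| 30 September 2021 | 63 / 277 | 23% | 42 / 0 |
| 31 December 2021 | 155 / 369 | 42% | 134 / 71 |
| 31 May 2022 (full) | 308 / 520 | 59% | 287 / 224 |

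These are shares of calendar days, not of participants.

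**Where the cut-offs might fall.** The only coverage figures are at one date: adult coverage "has reached 89.7% for the first dose, 87.6% for the second dose and 65.1% for the booster dose by June 14, 2022". As an illustration, assume a straight-line rise in first-dose coverage from S to 14 June 2022 (534 days).

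- 60%: 60/89.7 × 534 = day 357, 19 December 2021. L is 19 May 2021 (day 143), by when coverage is 143/534 × 89.7 = 24 points. So 24 of the 60 points could be positive for (iii).
- 80%: 80/89.7 × 534 = day 476, 17 April 2022. L is 17 September 2021 (day 264), a share of 264/476 = 55%, against 59% for the full period.

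A rollout faster in the first half of 2021 would move both dates earlier and could put the 60% date before 28 July 2021. A late-accelerating one would move them later. If coverage means the booster, 80% had not been reached two weeks after the planned end of follow-up, and 60% could lie close to that end.

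**Does the relative risk move, or only the proportion?** Take two groups with the same true spacing, one simply vaccinated 14 days later. All values here are assumptions: normal first-dose dates with medians at day 170 and day 184 and SD 50 days; 5% of gaps uniform on 213 to 330 days, the rest uniform on 42 to 100 days; denominator, those with a second dose by the cut-off. The ratio of observed long-gap proportions (later group over earlier group) is about 0.5 at 23 October 2021, 0.6 at 19 December 2021, 0.9 at 17 April 2022 and 0.95 at 31 May 2022. The true ratio is 1 throughout, so the drift comes from the window alone.

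**The case against.** The strongest objection is scope. The sentence on coverage cut-offs names no outcome. The plural in the Confounding bias section concerns infection adjustment and would be satisfied by the three uptake outcomes. Comparability with lower-coverage countries also suits uptake better than spacing. That is fair: inclusion of spacing is a reading. But it is the literal one. The introduction makes between-dose spacing a study aim, and nothing exempts it. If only uptake was meant, the remedy is to say so.

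The second objection is size, and it stands in part. A reader might infer that the spacing analyses at both levels must be empty, or rest on a handful of people. The documents do not support that, because they give neither the dates nor the coverage definition. In the straight-line illustration, 24 of 60 coverage points can still be positive at the 60% level, and the 80% level differs little from full follow-up. Nor is the straight line a bound in either direction.

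Third, a lower observed proportion does not by itself bias a relative risk; if vaccination timing did not differ by tobacco use, the ratio could hold. This is right in principle. The two-group illustration shows that a modest timing difference is enough to move the ratio, and whether uptake differs by tobacco use is what the study sets out to learn. It does not show the size or direction of the shift in the actual data.

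Finally, a model with no events fails visibly and misleads nobody. The cut-offs after July 2021 are the ones that could mislead.

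**Conclusion.** The point holds in a limited form. From the plan's own dates, spacing outcome (iii) cannot be estimated at any cut-off before 28 July 2021, and (iv) becomes possible only later. At any later cut-off short of the full period, the eligible group depends on the cut-off date, so a changed relative risk is not evidence that the association changed over time.

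This conclusion needs only the start date, the 7-month definition and the literal scope of the sensitivity analysis. The size does need information that the documents lack, and ranges from no estimable relative risk to a small shift.

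A reader might extend this to the study's main findings. That is not supported: the primary outcome is unaffected, and so are the uptake outcomes as far as this point goes. The full-period spacing estimates do not use the coverage cut-offs, although a milder form of the same limit applies to them, since an earlier dose on or after 31 October 2021 cannot show the gap by 31 May 2022. It is worth correcting because the correction is nearly free and prevents a specific misreading.

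**What to change.** Add one sentence to the sensitivity analyses under Statistical methods: the 60% and 80% coverage analyses apply to the uptake outcomes only, and spacing outcomes (iii) and (iv) are not analysed at those cut-offs.

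If change over time in spacing is of interest, analyse it on full follow-up by calendar period of the earlier dose. Define the event as no next dose within 7 months, and include only people whose earlier dose was at least 7 months before the actual end of follow-up. Tie that limit to the actual end rather than a fixed date, because the plan allows follow-up to run to the latest available date. The event needs this definition because a window of exactly 7 months cannot contain a completed gap of more than 7 months. It also counts people who never received the next dose, so it should be reported as a separate measure from (iii) and (iv).

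The cost is one sentence and, if the optional analysis is wanted, one extra table from dose dates already in the register. What is given up is the spacing estimates at the two cut-offs, which could not answer the question about change over time.
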